The finding that a single bolus of lidocaine could produce an analgesic effect of three weeks or more, has led one of the investigators (SJ) and a colleague to use single bolus lidocaine therapy for chronic, largely non-cancer pain in Kelowna. Intermittent intravenous lidocaine infusions of 5-9mg/kg over 1-2 hours have also been used routinely for severe opioid-resistant cancer pain at the Vancouver Centre by another investigator (PH) for approximately 8 years. In Kelowna we have a considerable body of experience of over 10 years with over 3000 Subcutaneous Lidocaine Infusions (SCLI). Our clinical experience suggested a useful analgesic response in approximately half the patients, lasting from days to several weeks. We did not encounter toxicity-related problems and did not feel that ECG monitoring was required. In our early experience in the Kelowna General Hospital (KGH) non-cancer pain population we converted 60 patients receiving Intravenous Lidocaine Infusion (IVLI) over 1-3 hours, to SCLI over 4-10 hours. We found that these patients experienced pain relief as good as, or better than, that obtained by IVLI. We saw no toxicity. We now use IVLI only for our cancer pain patients and about 10 non-cancer patients who have refused to change the route of administration. SCLI starting with 8-12mg/kg (less in the elderly) at 1.5mg/kg/hr has not been associated with side effects other than some mild somnolence. All patients go home with the infusion and we have had minimal calls because of adverse effects. We believe that SCLI is the appropriate route to investigate for the reasons outlined above i.e. decreased cost, complexity and toxicity. At the KGH Pain Clinic we administer about 15-18 SCILIs weekly and find that most of such patients experience 15-21 days of pain relief following each SCLI.

Despite our positive experience, there are no published studies of SCLI, and access to this treatment in BC is limited to the Kelowna area. We believe that a randomized placebo controlled trial of the use of SCLI in cancer patients with inadequately controlled pain would be of significant value and may lead to improved access to this potentially very useful treatment modality.

Study Objectives

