assessment tool which asks for pain severity over the 24 hours prior to completion, which makes it very suitable for repeated use in assessing response to lidocaine. It takes only a few minutes to complete. The pain assessment on the morning of the infusion will be the baseline point for determination of response in the study, but subjects will need to be familiar with it in order for repeated scoring throughout the study. Introducing the BPI at the baseline visit will allow it to be explained without the time pressure of needing to start the infusion.

At the baseline visit the subjects will be instructed as to discontinuation of their long-acting opioid on the morning of treatment as appropriate for the pharmacokinetics of the particular opioid: For those on Morphine, Oxycodone or Hydromorphone their long-acting dose will be omitted on the morning of the treatment, and the dose divided into three 4-hourly doses of the short-acting preparation of the same drug. In the absence of a response to treatment, the long-acting dose will be re-assessed at the end of the treatment day. If the subject does experience analgesia from the study drug then the dosing of the long-acting opioid will be adjusted as needed according to that response by telephone advice from the study physician.

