Final Visit: (post 2nd infusion, once the worst pain score on the BPI (question #3) has returned to baseline by phone assessment and minimum 48 hours and a maximum of three weeks since the return to baseline., At the final visit, the ,BPI, POS, Medication Use Log. Adverse Events Log and PPS will be reviewed

A positive response re: pain relief would be defined as any of the following:

- A 2-point reduction in worst pain intensity (#3 on the BPI) within 48 hours of infusion and lasting a minimum of 7 days
- Reduction in analgesic dose by greater or equal to 30% will also be considered an indicator of positive response.

Statistical Considerations: **Objective**

To compute the power and sample size calculation for the study

Assumptions

- Probability of response in the placebo group = 30%
- There is no carry-over effect, no period effect and no sequence effect in the study

- 0.01% of the patients who did not respond to the lidocaine will respond to the placebo

Null Hypothesis: There is no difference between a single infusion of subcutaneous lidocaine and the placebo

Alternative Hypothesis: A single infusion of subcutaneous lidocaine can cause a reduction in cancer pain

Sample Size / Interim Analysis

A sample size of 40 patients achieves 84% power to detect a 20% difference at a 2.5% significance level using a one-sided McNemar's Test, under the assumptions that 30% of the patients respond to the placebo and 0.01% of the patients who do not respond to the lidocaine will respond to the placebo. This sample size is increased to 50 patients to account for a 20% drop-out rate. This drop-out rate is based on our experience accruing similar patients to studies. The sample size methodology is based on the methodology described in Lachenbruch 1992.

We have demonstrated in the completed Feasibility Study for a Randomized Double Blind Placebo Controlled Crossover Trial of the Use of Subcutaneous Lidocaine Infusion for Chronic Cancer-related Pain that recruitment to such a study is feasible, and that we should expect this study to take 6 months for accrual.

An interim analysis will be carried out after 20 patients have completed the study to allow the trial to be stopped early for demonstrated efficacy. One-sided McNemar's tests will be carried out to test whether a single infusion of subcutaneous lidocaine will cause a reduction in cancer pain for both the interim and final analyses at the p-values of 0.00153 and 0.02347 respectively.

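### Is 40 completers too few because the plan assumes that almost nobody responds to placebo alone?

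*Combined protocol and SAP*

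**What the plan says.** In the combined protocol and SAP, the Assumptions list under Statistical Considerations sets placebo response at 30%, excludes carry-over, period and sequence effects, and adds that "0.01% of the patients who did not respond to the lidocaine will respond to the placebo".

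Sample Size / Interim Analysis repeats these inputs and concludes: "A sample size of 40 patients achieves 84% power to detect a 20% difference at a 2.5% significance level using a one-sided" McNemar's test. It continues: "This sample size is increased to 50 patients to account for a 20% drop-out rate". There is one efficacy look after 20 completers, with testing "for both the interim and final analyses at the p-values of 0.00153 and 0.02347 respectively". The section does not say whether the McNemar test is exact, mid-p, continuity-corrected or uncorrected.

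The drop-out rate is attributed to experience and the sample-size method to a publication. The completed feasibility study is cited to show that recruitment is feasible and that "we should expect this study to take 6 months for accrual". It appears again in Notes on Outcome Measures, which says that the quality-of-life questionnaire was used in it. No source is shown for the 0.01%.

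**The concern.** In a paired binary design only discordant patients carry information. The power therefore depends on how many patients respond to placebo but not to lidocaine, as well as on the 20-point difference. The plan sets that number practically at zero: placebo works in 60% of lidocaine responders but in 1 of 10,000 non-responders.

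The design leaves room for placebo-only responders. Clinical Experience reports that "Our clinical experience suggested a useful analgesic response in approximately half the patients", so many patients may not respond to lidocaine. Under Baseline Visit, "The pain assessment on the morning of the infusion will be the baseline point for determination of response in the study", and the pain inventory is repeated before each infusion. The second infusion may come up to three weeks after pain has returned to baseline. Either a 2-point fall in worst pain or a 30% fall in opioid dose counts as response. A patient could meet the endpoint after placebo and miss it after lidocaine.

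If that happens even occasionally, the true power is below 84%, and a null result from 40 completers could be read as lack of benefit when the trial was simply too small.

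**Working it through.** **Inputs.** From the Assumptions list and Sample Size / Interim Analysis: placebo response 0.30; difference 0.20, so lidocaine response 0.50; placebo-only rate among lidocaine non-responders q = 0.0001; 40 completers; final one-sided level 0.02347; drop-out 20%. Values of q from 1% to 30% are assumptions, because the documents give none.

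**What q = 0.0001 implies.**
- Placebo only: 0.50 × 0.0001 = 0.00005 of all patients; 40 × 0.00005 = 0.002 expected.
- Both respond: 0.30 − 0.00005 = 0.29995.
- Lidocaine only: 0.50 − 0.29995 = 0.20005.
- Placebo response among lidocaine responders: 0.29995 / 0.50 = 0.5999.
- Chance of at least one placebo-only patient in 40: 1 − (1 − 0.00005)^40 = 0.0020.

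**Reproducing the plan's 84%.** With no placebo-only pair, the exact one-sided p-value for b lidocaine-only pairs is 0.5^b. Five pairs give 0.03125, which is too large. Six give 0.015625, which is enough at 0.02347 and at 0.025. P(Bin(40, 0.20) ≥ 6) = 0.8387, and the full calculation at q = 0.0001 gives 0.8383. A continuity-corrected test also gives 83.8%, and the interim look does not change it. The stated figure is right.

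**Varying q with the difference kept at 20 points.** Placebo-only probability p01 = 0.5q; lidocaine-only p10 = 0.20 + 0.5q. The discordant count n follows Bin(N, p10 + p01). Given n, the lidocaine-only count b follows Bin(n, p10 / (p10 + p01)). The exact test rejects when P(Bin(n, 0.5) ≥ b) ≤ 0.02347.

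| q | 40, exact | 40, mid-p | 40, uncorrected | 50, exact |
|---|---|---|---|---|
| 0.01% | 83.8% | 92.4% | 97.1% | 95.2% |
| 1% | 80.1% | 89.1% | 92.4% | 92.2% |
| 2% | 76.7% | 85.9% | 88.2% | 89.2% |
| 5% | 67.8% | 77.3% | 78.1% | 80.6% |
| 10% | 56.2% | 65.4% | 66.3% | 68.2% |
| 30% (independent responses) | 33.9% | 41.3% | 42.4% | 43.8% |

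At q = 5% the expected placebo-only count is 40 × 0.5 × 0.05 = 1. With the exact test, one such pair raises the lidocaine-only pairs needed from 6 to 8 (7 against 1 gives p = 0.035; 8 against 1 gives 0.0195).

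**Dependence on the effect.** At a 25-point difference (lidocaine 55%, so p01 = 0.45q), exact power with 40 completers is 96% at q = 0.01%, 85% at 5% and 75% at 10%.

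**Type I error.** With 40 completers the maximum over both looks is 0.0197 for the exact test and 0.0225 for mid-p. At the final level alone, the uncorrected test reaches about 0.024. All are below 0.025.

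**What enlarging would cost and buy.** Fifty completers need 50 / 0.80 = 62.5, so 63 enrolled. That is 13 more patients (13/50 = 26%) and, at 50 patients in 6 months, 63 × 6/50 = 7.6 months, or 1.6 more. Exact power at 50 completers is at least 80% only up to q of about 5%. With mid-p, 43 completers (43 / 0.80 = 53.75, so 54 enrolled) already give 80.7% at q = 5%, so the extra number depends on the test version as much as on q.

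**The case for a change.** The strongest opposing argument is that 0.01% lies at the favourable end of the range, so any departure lowers power. Exact power with 40 completers falls below 80% once q passes about 1.0%, which is 0.2 expected patients. A rate of 5% is only one sixth of the 30% that independent responses would give, yet it doubles the chance of missing a true 20-point effect from 16% to 32%. On that view, an undefended number should not set the enrolment.

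Much of this stands. No source for the 0.01% is shown, the arithmetic is correct, and 84% is close to the most an exact test can reach with 40 completers at 20 points (83.9% at q = 0).

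It does not lead to a different number. The case for 63 rests on q = 5%, which is no better documented. The design features show that placebo-only response is possible, not how common it is. Other features work against chance responses: onset within 48 hours, a seven-day minimum, and no new adjuvant analgesic or procedure during the study. The half-response figure comes from uncontrolled experience in largely non-cancer pain. The feasibility study collected at least quality-of-life data, so one cannot say that the sponsor had no outcome data from it, only that none are shown.

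Naming the exact test would settle a detail and cost power: at q = 5% it gives 68%, against 77% (mid-p) and 78% (uncorrected), and all three hold type I error with 40 completers. Printing a sensitivity range beside the 84% would inform the reader but alter neither the enrolment, the analysis nor any result.

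**Conclusion.** The plan can stand. Its 84% is correct for inputs that it declares, and the sample size follows from them. The placebo-only assumption is optimistic and no support for it is shown. If the true rate among lidocaine non-responders were 1% to 10%, exact power with 40 completers would be 80% to 56% at a 20-point difference, and higher with a less conservative McNemar version or a larger effect. Those rates are assumptions, and the documents offer no basis for choosing one and resizing the trial around it.

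The unnamed test version is a gap that analysts can fill sensibly. The reported 84% points to an exact or continuity-corrected test, and the versions checked keep the error rate below 2.5% with 40 completers.

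The point bears on interpretation. A non-significant result should be judged by the confidence interval and the observed discordant pairs, not by the 84%. The sizing risk is a fair trade-off for a small crossover trial and does not affect the validity of a positive result.

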At 1000 am on Day 2 and Day 3, the BPI and POS will be completed. If there is a reduction in pain scores, the BPI and POS will continue to be completed on Day 7, 14 and 21 post each infusion, or until the worst pain score on the BPI #3 has returned to baseline. If there is no change, the questionnaires for Day 7 will be completed and the patient will be scheduled for the next follow up visit and treatment within a minimum of 48 hours and maximum of three weeks of the pain returning to baseline. The Medication Use Log is to be completed daily, and the Adverse Events Log completed if an adverse event occurs. Telephone contact will be made at a minimum twice a week until the pain is back to the pre-treatment level by the research nurse or physician and to adjust medications if necessary, and, once pain returned to baseline, once weekly telephone contact will be done til the 2nd treatment visit to review any condition or medication changes. Subjects will also be encouraged to call the physician at any time if they experience any adverse event or to report return to baseline pain score.

Once the worst pain score on the BPI (question #3) has returned to baseline and at least 48 hours have elapsed, the second treatment will be arranged. If there is a response the patient will continue with diaries and questionnaires weekly until the BPI score returns to baseline

Second Treatment Visit

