The assumptions of no carry-over effect, no period effect and no sequence effect are made under this study. To check these assumptions, a repeated measures logistic regression model will be fitted to model the probability of pain reduction by treatment type (placebo versus lidocaine), stratifying by the treatment order (first or second treatment). This model accounts for inter-subject variation and within-subject correlation. Score tests will be used to test whether the treatment order estimate equals to zero at a 5% significance level. Rejection of this null hypothesis implies a carry-over effect, period effect and sequence effect.

Safety Considerations:

Any subject with unrecognized allergy to lidocaine would be expected to react within the first hour, and subjects will be closely observed during that

time. Any later side-effect will be able to be addressed promptly by the patient returning to the Cancer Centre for assessment by the nurse and/or physician. There is an emergency response team in the cancer centre during working hours and the study physician will be available for the duration of all infusions.

References:

1. Bartlett EE and Hutaserani O. Xylocaine for the relief of postoperative pain. *Anesth Analg* 1961; 40:296-304.
2. Edmondson EA et al. Systemic lidocaine therapy for post-stroke pain. *Southern Medical Journal* Oct 1993 86(10):1093-1096
5. Strichartz G. Protracted Relief of Experimental Neuropathic Pain by Systemic Local Anesthetics: How, Where, and When. *Anesthesiology*: Volume 83(4) October 1995 pp 654-655.

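### One 'treatment order' coefficient cannot test carry-over, period and sequence effects together, so the plan's reading of a rejection is wrong

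*Combined protocol and SAP*

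**What the plan says.** Under 'Statistical Considerations', the list of assumptions includes: "There is no carry-over effect, no period effect and no sequence effect in the study". The check comes in the last paragraph before 'Safety Considerations': "To check these assumptions, a repeated measures logistic regression model will be fitted to model the probability of pain reduction by treatment type", with one further factor, "stratifying by the treatment order (first or second treatment" (the bracket closes there). The decision rule is: "Score tests will be used to test whether the treatment order estimate equals to zero at a 5% significance level". The conclusion attached to it is: "Rejection of this null hypothesis implies a carry-over effect, period effect and sequence effect".

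No sequence term, treatment-by-period term or second test is described, and no action is attached to either outcome. The primary analysis is a one-sided McNemar test at the interim and final looks. Protection against carry-over comes from the design. Under 'Between Visits', the second infusion is arranged only at this point: "Once the worst pain score on the BPI (question #3) has returned to baseline and at least 48 hours have elapsed".

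**The concern.** Carry-over, period and sequence effects are different things with different consequences. In a two-sequence, two-period design a pure period effect is largely balanced out of the treatment comparison. A pure sequence effect cancels within patients. A difference in carry-over between the two treatments biases the estimate. A one-degree-of-freedom test cannot tell these apart.

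Two misreadings follow. If the test rejects because of a period effect alone, the plan's sentence would have the report announce carry-over and sequence effects for which there is no evidence, casting doubt on a sound result. If it does not reject, a reader is likely to take three assumptions as checked when at least one could not have been detected. Carry-over deserves care here because the background sections expect relief lasting days to weeks after one infusion.

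**Working it through.** **1. The plan's own figure.** Inputs from 'Assumptions' and 'Sample Size / Interim Analysis': 40 completers, placebo response 30%, difference 20 points (so lidocaine 50%), one-sided 2.5%, and "0.01% of the patients who did not respond to the lidocaine will respond to the placebo". Then P(placebo response only) = 0.0001 × 0.50 = 0.00005 and P(lidocaine response only) = 0.20005. The exact one-sided McNemar test has 83.8% power, matching the stated 84%. Enrolment is 40/(1 − 0.20) = 50, as stated: "This sample size is increased to 50 patients to account for a 20% drop-out rate". The sample size is not in question.

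**2. What the coefficient estimates.** On the additive scale let τ be the treatment effect, π the period effect, cL and cP the carry-over from lidocaine and placebo, and s the shift of the placebo-first group.

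| Sequence | First infusion | Second infusion | Second minus first |
|---|---|---|---|
| Lidocaine first | μ + τ | μ + π + cL | π + cL − τ |
| Placebo first | μ + s | μ + s + π + τ + cP | π + cP + τ |

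- Order (first/second) = average of the last column = π + (cL + cP)/2. Weight on s: zero.
- Treatment = half the difference (placebo-first minus lidocaine-first) = τ − (cL − cP)/2.
- Between-sequence contrast of patient totals (lidocaine-first minus placebo-first) = cL − cP − 2s. Weight on π: zero.

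The quantity that biases treatment, cL − cP, also appears in the between-sequence contrast, where it is aliased with sequence (and with treatment-by-period interaction). In the order coefficient only the sum cL + cP appears, mixed with π. With equal sequence sizes and a working-independence logistic model containing treatment, the numerator of the score test for order is proportional to the sum of the two sequences' mean second-minus-first differences, so this algebra carries over to the planned test.

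**3. Rejection rates, first/second coding.** The effect sizes, 1:1 allocation and correlations are assumptions, used as stress cases and not as predictions. Robust GEE logistic score test at 5%, 20 completers per sequence, 50% versus 30%, 20,000 replicates; latent within-patient correlation 0, 0.3, 0.6, and fully nested responses.

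| Scenario | 0 | 0.3 | 0.6 | Nested | Treatment difference |
|---|---|---|---|---|---|
| No effects | .053 | .050 | .053 | .049 | 20 points |
| Period −10 points | .163 | .182 | .218 | .355 | 20 |
| Period −20 points | .520 | .585 | .680 | .983 | 20 |
| Sequence +20 points | .050 | .051 | .049 | .050 | 20 |
| Equal carry-over +10 from both | .154 | .171 | .208 | .361 | 20 |
| Lidocaine carry-over, placebo 30→40% | .080 | .083 | .088 | .140 | 15 |
| Lidocaine carry-over, placebo 30→50% | .148 | .173 | .205 | .589 | 10 |
| 30→50% with period −5 | .077 | .080 | .087 | .162 | 10 |
| 30→50% with period −10 | .050 | .052 | .052 | .048 | 10 |
| 30→50% with period −15 | .077 | .083 | .089 | .167 | 10 |

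The −10 row is a knife edge: −10 + 20/2 = 0, so the coefficient is exactly zero while the treatment difference is halved.

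**4. Rejection rates, sequence coding.** A period decline of 10 or 20 points rejects in 5.0% to 5.6% of trials, about the null level. Carry-over 30→50% rejects in .152/.138/.124/.103.

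**5. Effect on the primary test.** Under nested responses all discordant pairs favour lidocaine, and six are needed at 0.02347, because (1/2)^6 = 0.0156 and (1/2)^5 = 0.031. With no period effect, power is .839. With a 10-point decline the discordance probabilities are .50 − .20 = .30 (lidocaine first) and .40 − .30 = .10 (placebo first), and power is .847. A pure period effect therefore does not undermine the McNemar test.

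**6. Precision of a first-infusion comparison.** The 95% half-width is 1.96 × √(.25/20 + .21/20) = .297 with 20 versus 20, and 1.96 × √(.25/25 + .21/25) = .266 with 25 versus 25. Power at one-sided 2.5% is .163 (Fisher) to .245 (z), and .232 to .334, respectively.

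**The case against.** The strongest reply is that nothing hangs on this check. The plan attaches no action to it, the McNemar test is run regardless, and the plan never says that non-rejection validates the assumptions. The last sentence might also have been meant as 'at least one of the three'. This limits the harm to interpretation, but it does not rescue the rule. Under the looser reading one of the three effects still has zero weight, and the paragraph presents the test as the check on all three.

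Three narrower points stand:

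- Missing a pure sequence effect does no damage to the treatment estimate, since s cancels within patients. The objection is to claiming to have tested it.
- The order test is not weaker than a between-sequence test for one-sided lidocaine carry-over. With cP = 0 and the 30→50% scenario its power is similar or better (.148 to .589 against .152 to .103). Its defect is that it cannot separate that carry-over from a period effect.
- The direction of any carry-over bias is unknown. Response is scored against pain on the morning of the infusion, so residual relief could lower the second baseline and make a 2-point drop harder. If second-period placebo response fell from 30% to 20%, the difference would rise to 20 + 10/2 = 25 points, flagged in about 8% to 11% of trials.

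It can also be said that correcting the sentence is enough and the extra estimates are optional. The sentence is indeed the error. The two added estimates are what let a reader judge period and carry-over once the test no longer claims to do so.

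**Conclusion.** The concern holds. The aliasing follows from the design and needs no assumed figures: under either coding, rejection cannot establish all three effects and non-rejection cannot support all three assumptions. The size depends on assumed effects and correlation. With 20 completers per sequence and first/second coding, a harmless 10-point period decline would be labelled carry-over in 16% to 36% of trials (52% to 98% for 20 points). A lidocaine carry-over that halves the difference would be flagged in 15% to 59%, and in as few as 5% if a period decline offsets it.

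The consequence is for what the report may say about the crossover assumptions. The primary test, sample size and power are unaffected. The wait for pain to return to baseline plus at least 48 hours is the real protection, and any residual carry-over cannot be determined from the documents. The text should be corrected, but the error does not invalidate the trial.

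**What to change.** Delete the sentence on what rejection implies. In its place, state that the order coefficient (first versus second infusion) estimates the period effect plus any average carry-over, cannot separate them and does not test sequence effects. State also that its p-value will not be used to validate or choose the analysis.

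Whatever that p-value, report beside the McNemar test, each with a 95% confidence interval:

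1. The period-adjusted treatment effect from the logistic model already planned, specified as population-averaged (GEE) with robust standard errors. It handles period but not carry-over.
2. The first-infusion-only comparison of lidocaine with placebo, in all patients with first-infusion outcome data. It is free of carry-over and should be labelled a consistency check.

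The cost is wording and two outputs from data already collected. The drawback is imprecision: the first-infusion interval is about ±30 points with 40 completers and about ±27 with all 50 enrolled, and its power is 16% to 33%, so it cannot replace the primary test.
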